3.1. Participants

Twenty four healthy, normal-weight (BMI 18.5–25 kg/m²) females, aged 21–24 years, were recruited from Erciyes University and the surrounding community. Exclusion criteria were following an energy-restricted diet during the last three months, change in body weight >5 kg during the last three months, lack of appetite, physician-diagnosed conditions or medications that influence metabolism, having any chronic diseases such as diabetes, hypertension etc., smoking, practicing endurance sports, having difficulties with swallowing/eating, hypersensitivity for the food products under study, being a vegan, and pregnant or lactating. Furthermore, one enrolled participant withdrew from the trial and the other one was not

included to the analysis of data because of influenza. Finally, leaving a total of 22 participants were assessed for the main outcomes (Fig. 1).

[figure not shown]

Figure 1. Participant recruitment flow diagram

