3.3. Study design

This was a randomized, single-blind, 3-intervention crossover trial conducted on 3 separate days, with a 1-week washout period between each study day. All participants were randomly submitted to three different test meals with the following different GI amounts and milk or kefir: a low-GI and milk content (LGI-Milk), a low-GI and kefir content (LGI-Kefir), and a high-GI and kefir content (HGI-Kefir). The order of the test meals was determined by using a computer-generated randomization sequence before recruitment. The primary outcomes were appetite sensations and subsequent food intake. Desire for specific food types and palatability of test meals were the secondary outcomes.

Participants received each test meal in a randomly assigned order on three different mornings separated by a washout period of 1-week when they were asked to maintain their usual diet and physical activity. On the day before each test meal, participants were instructed to eat a standard evening meal at 21:00 h and to refrain from eating and/or drinking (except for water) and/or doing any physical activity beyond that of their typical daily activities. Moreover, participants were tested within the follicular phase of their menstrual cycle (3–10 d after onset of menses) to avoid possible influences of menstrual cycle phase on hormonal changes and appetite (Chowdhury, Richardson, Tsintzas, Thompson, & Betts, 2015).

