On the each testing day, participants arrived in the testing room at 08.30 h following a 12-h fast and anthropometric measurements were completed before eating the test meal. Also, first appetite scores were measured for baseline measurements (time zero). At 09:00 h participants received the test meal blinded to its nutritional characteristics and were asked to consume within 15 min. During the postprandial period, participants remained at rest in the testing room and appetite scale was applied at 15, 30, 60, 90, 120, 150 and 180 min. Moreover, participants were asked to assess the palatability of test meal at 15 min (immediately after consuming test meal). No food or drink other than water was allowed following consumption of the test meal until an ad libitum lunch. Water was available ad libitum throughout the first trial; however, the volume consumed was measured and the participants drank the same volume during the second and third trial. Participants were permitted to watch movies, read, or play with electronic devices (laptop computer, mobile phone etc.) or undertake other similar sedentary activities throughout each test day but were not allowed to sleep.

This study was conducted according to the guidelines laid down in the Declaration of Helsinki. All procedures were approved by the Clinical Research Ethics Committee of the Erciyes University (2016/547) on 21 October 2016, and all participants gave written informed consent. In addition, it was registered at ClinicalTrials.gov as NCT03636217.

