4.2. Data analysis

Statistical analysis was performed using the Statistical Package for the Social Sciences (version 22.0; IBM SPSS Statistics) software. Data were expressed as the mean \pm SD unless otherwise indicated. Normality was assessed using the histogram and normal Q-Q plots, and also Shapiro-Wilk test. Furthermore, continuous variables were examined for skewness and kurtosis, and log-transformed before analysis and reported back-transformed geometric means (G) \pm standard error (S.E) when required (Akin, et al., 2015). Postprandial appetite sensations were quantified as area under the curve (AUC) calculated according to the trapezoidal rule. One-way (1-factor) analysis of variance (ANOVA) for repeated measures was applied to determine statistical differences between groups. In addition, the data were analysed by using 2-factor (time x meal) repeated-measures ANOVA, and Bonferroni post hoc tests were applied to significant time x

meal interactions. For all statistical analyses, p values less than 0.05 were considered to have statistical significance.

REFERENCES

Chang, K. T., Lampe, J. W., Schwarz, Y., Breymeyer, K. L., Noar, K. A., Song, X., & Neuhouser, M. L. (2012). Low glycemic load experimental diet more satiating than high glycemic load diet. *Nutr Cancer*, 64, 666-673.

Chowdhury, E. A., Richardson, J. D., Tsintzas, K., Thompson, D., & Betts, J. A. (2015). Carbohydrate-rich breakfast attenuates glycaemic, insulinaemic and ghrelin response to ad libitum lunch relative to morning fasting in lean adults. *Br J Nutr*, 114, 98-107.

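### Section 4.2 relies on repeated-measures ANOVA with no missing-data rule, so a woman drops out of any outcome with one value missing; a mixed model would keep her usable sessions

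*Combined protocol and SAP*

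**What the plan says.** Section 3.3 sets three sessions per woman ("This was a randomized, single-blind, 3-intervention crossover trial conducted on 3 separate days"). Ratings are taken at time zero, and then "appetite scale was applied at 15, 30, 60, 90, 120, 150 and 180 min". Appetite sensations and subsequent food intake are both primary outcomes. Section 3.6 adds a composite score built from four scales at each time point.

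Section 4.2 names two inferential methods. The first is one-factor: "One-way (1-factor) analysis of variance (ANOVA) for repeated measures was applied to determine statistical differences between groups". The second covers the time course: "In addition, the data were analysed by using 2-factor (time x meal) repeated-measures ANOVA". The software is "Statistical Package for the Social Sciences (version 22.0; IBM SPSS Statistics) software", with no procedure or missing-value option named. The summary measure is the AUC: "Postprandial appetite sensations were quantified as area under the curve (AUC) calculated according to the trapezoidal rule". The documents contain no missing-data rule, no rule for an AUC with a gap, and no definition of the analysis set.

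Section 3.1 reports that "one enrolled participant withdrew from the trial" and that a second woman was left out of the analysis because of influenza, leaving 22. Section 4.1 gives a need of 21 women and 24 recruited to allow for losses.

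**The concern.** A classical repeated-measures ANOVA works on a complete woman-by-cell table. A woman with one empty cell leaves that model, including comparisons for which her data are complete. A woman with both low-GI sessions and no high-GI session carries full information on kefir against milk, which is the direct test of the study's aim, yet the three-meal ANOVA cannot use her.

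At stake are precision in a small trial and clarity about who is in each analysis. The number analysed could differ between scales, between the AUC and the time course, and between lunch intake and appetite, with no rule saying how.

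**Working it through.** **1. The plan's own figures.** The 21 in section 4.1 cannot be reproduced, because no SD or within-woman correlation is given. Solving backwards for a two-sided paired t-test (alpha 0.05, 80% power, n = 21; sidedness assumed) gives a standardised difference of 0.643. For a 5% difference that is an SD of within-woman differences of 5/0.643 = 7.8%. For the loss allowance, 21/0.85 = 24.7 and 21 x 1.15 = 24.15, so 24 is about right. Actual loss was 2/24 = 8.3%, inside the 15% allowed.

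**2. Values each analysis needs per woman.**
- Lunch intake: 3 (one per session). AUC of one scale: 3.
- Time x meal for one scale: 8 times x 3 sessions = 24.
- Time x meal for the composite: 4 scales x 24 = 96 marks.

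| Missing | Lunch intake | AUC, that scale | Time x meal, that scale | Composite, time x meal | Other scales |
|---|---|---|---|---|---|
| One session | dropped | dropped | dropped | dropped | dropped |
| One VAS mark | kept | depends on an unstated gap rule | dropped | dropped | kept |

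**3. What partial sessions are worth for kefir against milk.** Assume a random-intercept model with session variance s². Each woman with both low-GI sessions supplies one difference with variance 2s², whether or not she has the high-GI session.
- 22 complete women: 2s²/22.
- One more with both low-GI sessions: 2s²/23, a reduction of 1 - 22/23 = 4.3%.
- Two more: 2s²/24, a reduction of 1 - 22/24 = 8.3%.

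These figures do not depend on the intraclass correlation. Other patterns do. Generalised least squares at assumed correlations of 0.3 to 0.9, for two women added to 22, gives:
- two sessions each, one woman holding both meals of the contrast and the other not: equivalent to 23.3 to 23.4 complete women;
- two sessions each, neither holding both meals of the contrast: 22.5 to 22.8;
- one session each: 22.0 to 22.7;
- no usable session: 22.

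At the back-solved effect, power is 80.0% with 21 women, 82.0% with 22, 83.8% with 23 and 85.4% with 24.

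**4. Missed marks, as illustration only.** No missed mark is reported. If marks were missed independently with probability p, the share of women complete is (1 - p)^24 per scale and (1 - p)^96 for the composite.

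| Assumed p | Per scale: share, of 22 | Composite: share, of 22 |
|---|---|---|
| 0 | 1.000, 22 | 1.000, 22 |
| 0.1% | 0.976, 21.5 | 0.908, 20.0 |
| 0.5% | 0.887, 19.5 | 0.618, 13.6 |
| 1% | 0.786, 17.3 | 0.381, 8.4 |

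Clustering of missed marks within a few women would make the loss smaller.

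**5. Would a mixed model alter a complete-data result?** For lunch intake and AUC, a model with meal and a random woman effect reproduces the one-factor ANOVA (provided the estimated woman variance is positive), so only the added period term changes anything. For ratings it may differ. The two-factor ANOVA tests meal against woman-by-meal variation, and a mixed model without a session effect does not. In simulated complete data (22 women, 3 x 8 ratings, woman-by-meal variation present), a random woman effect plus AR(1) within session moved the meal F from 1.25 to 1.83 in one data set and from 2.74 to 4.11 in another. The session effect is therefore needed, or the meal test can be too liberal.

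**The case against.** The strongest case against is that nothing documented shows harm. Ratings were made at rest in the testing room with a fresh booklet each time, so missed marks may be rare or absent. The 22 women analysed exceed the 21 required. The two lost women may have had no usable session. On that view the choice of model is preference, and only the analysis set and a rule for missing marks need stating. This limits the size of the point. It does not remove it, because the plan is silent and the better method is cheap.

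Several stronger readings are tempting, and the documents do not support them.
- A reader might infer that one missed mark costs all of a woman's data. Deletion is per model, so lunch intake and the other scales survive. Deletion itself is inferred from the method; the text does not state it.
- A reader might take 22 against 21 as the planned margin. The plan recruited 24 against 21; 22 is what remained.
- A reader might expect large losses. That rests on assumed rates for missed marks, or on several of the 22 lacking a session, which nothing suggests. If five of 22 did lack one session each, the variance saving against the 17 complete women would run from about 6% to 23% depending on which sessions were missing, so no single figure is defensible.
- A reader might conclude that the ANOVA is biased whenever loss relates to response. Loss tied to a woman's stable level cancels in within-woman contrasts; loss tied to how she responded in a particular session is what matters.
- A reader might blame the ANOVA for the influenza exclusion. That was the investigators' decision, and a new model alone would not reverse it.

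**Conclusion.** The point holds as an inexpensive improvement. Section 4.2 gives no missing-data rule, and its ANOVAs discard a woman from any outcome with an incomplete set of values. Two of 24 women contribute nothing to the main outcomes, and their completed sessions are not reported.

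The gain for kefir against milk lies between nil (no usable partial sessions) and about 8% of the variance (both women with both low-GI sessions), if they are the only partial data. The upper end corresponds to power of 85.4% against 82.0%, on the back-solved effect. These figures assume a random-intercept model, and that the session data of a woman who left early or was excluded are usable. A material loss from missed marks cannot be shown or excluded.

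**What to change.** - **Lunch intake and AUC:** linear mixed model (REML, Satterthwaite degrees of freedom) with fixed meal and period and a random woman effect. Period is needed because withdrawal empties later sessions and unbalances meal against period.
- **Ratings:** fixed meal, time, meal x time and period; random woman and woman-by-meal (session) effects; and a pre-specified within-session covariance structure.
- **Analysis set:** every randomised woman with at least one completed test session, with an explicit statement of how the influenza case is handled and why. Report the sessions and marks available for each outcome.
- **AUC:** bridge an isolated missing interior mark by the trapezoid between the neighbouring times. Also state what happens if the first or last mark is missing.
- **Sensitivity:** keep the planned repeated-measures ANOVA on complete women.

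The cost is SAP wording and a few lines of syntax in the same software, with no new data. The downsides are that a covariance structure must be fixed in advance and that the model assumes data are missing at random. With complete data, the lunch and AUC results change only through the period adjustment; the ratings F tests may differ from the ANOVA.

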3.4. Test meals composition

All test meals were matched for energy, LGI-Milk and LGI-Kefir meals also for macronutrients and GI, but HGI-Kefir meal had a nearly 2-fold difference in GI (Table 1). Furthermore, both milk and kefir drinks contained 120mg/100ml calcium, and kefir drink also had 107 CFU/g

probiotic bacteria (*Lactobacillus* spp. and *Streptococcus* spp.). The energy content of test meals (~445 kcal) were estimated as corresponding to about 25% daily energy needs of a sedentary female (Chowdhury, et al., 2015), and the daily energy needs were also calculated by the Schofield equation, taking into account: gender, age, weight and a physical activity level of 1.3.

Table 1. Nutritional composition and glycaemic index of the component foods in test meals

	Portion size (g/ml)	Energy (kJ[kcal])	AvCHO* (g)	Protein (g)	Fat (g)	GI (%)
LGI-Milk						
Milk (full-fat)	200	524(125)	9.9	5.8	6.8	31
Cheddar cheese	25	424(101)	0.0	6.4	8.5	0
Apple	200	469(112)	24.9	0.9	0.9	36
Grain bread	50	435(105)	19.1	4.8	0.9	50
Toplam		1852(443)	53.9	17.9	17.1	40
LGI- Kefir						
Kefir (full-fat, plain)	200	526(126)	10.0	5.8	6.3	36
Cheddar cheese	25	424(101)	0.0	6.4	8.5	0
Apple	200	469(112)	24.9	0.9	0.9	36
Grain bread	50	435(105)	19.1	4.8	0.9	50
Toplam		1854(444)	54.0	17.9	16.6	41
HGI- Kefir						
Kefir (full-fat, plain)	200	526(126)	10.0	5.8	6.3	36
Raspberry jam	50	568(136)	31.8	1.7	0.0	78
White bread	75	773(185)	34.0	7.0	1.5	70
Toplam		1868(447)	75.8	14.5	7.9	70

*AvCHO, available carbohydrate including sugars and starch, excluding fiber.

GI of foods in test meals was estimated by using the GI tables, with glucose as the reference food (Bao, Atkinson, Petocz, Willett, & Brand-Miller, 2011). The average meal GI was calculated as follows:

$$\text{Meal GI} = \frac{\sum_{a=1}^N (\text{GI}_a \times \text{AvCHO}_a \times \text{Frequency}_a)}{\sum_{a=1}^N (\text{AvCHO}_a \times \text{Frequency}_a)}$$

where n is the number of foods consumed, GI_a is the GI for food a, AvCHO_a is the available carbohydrate content per serving of food a, and Frequency_a is the consumption frequency of one serving of food a during the meal.

3.5. *At libitum lunch*

At 180 min after the test breakfast, participants were presented with the ad libitum lunch following appetite measurements. Frequently consumed foods were used to prepare the lunch consisting of pasta with tomato sauce, yogurt drink and mandarin. Participants were asked to

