4.1. Sample size

A power-based sample size calculation based on previous research from Stevenson et al. (Stevenson, Astbury, Simpson, Taylor, & Macdonald, 2009) revealed that 21 participants were needed to provide 80% power to detect 5% difference between groups in primary outcomes. To allow discontinuation during the study, 24 participants (considering 15% losses) were recruited, and the study was concluded with 22 participants.

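### Section 4.2 follows the time x meal interaction with single-step Bonferroni tests and names no contrasts; two named contrasts with Holm would give the kefir comparison more power at the same 5% family-wise error.

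*Combined protocol and SAP*

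**What the plan says.** Section 3.3 defines three meals: "a low-GI and milk content (LGI-Milk), a low-GI and kefir content (LGI-Kefir), and a high-GI and kefir content (HGI-Kefir"). Section 3.4 describes the matching. All three share energy content, with "LGI-Milk and LGI-Kefir meals also for macronutrients and GI, but HGI-Kefir meal had a nearly 2-fold difference in GI". There is no high-GI milk meal.

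Section 4.2 has two analyses. A one-way repeated-measures ANOVA tests for differences between meals, and no follow-up is named for it. A two-factor (time x meal) repeated-measures ANOVA is also run, after which "Bonferroni post hoc tests were applied to significant time x" meal interactions. The section does not list the pairs, give the number of comparisons or name a contrast of interest. The threshold is that "p values less than 0.05 were considered to have statistical significance".

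Section 4.1 states that "21 participants were needed to provide 80% power to detect 5% difference between groups in primary outcomes", citing an earlier study without giving an SD, and that "the study was concluded with 22 participants".

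**The concern.** The objective in Section 2 concerns kefir. Only LGI-Kefir versus LGI-Milk changes the drink while holding the rest of the meal fixed. HGI-Kefir versus LGI-Kefir holds the drink fixed and changes the solid foods, and so GI. HGI-Kefir versus LGI-Milk changes both: a difference could come from either source, and a null result could be two effects cancelling.

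If the Bonferroni family is the three pairs, each is tested at 0.05/3 = 0.0167, and part of the error rate goes to a pair that separates nothing. Single-step Bonferroni is also dominated within any family. Holm tests the smallest p-value at the Bonferroni threshold and relaxes the threshold after each rejection, so it controls the same error and rejects at least as much. With 22 women, what is at stake is power on the comparison that bears directly on the objective.

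**Working it through.** **1. What changes between meals (Table 1, Section 3.4, meal totals)**

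| Pair | Drink | GI | Fat (g) | Available carbohydrate (g) |
|---|---|---|---|---|
| LGI-Kefir vs LGI-Milk | changes | 41 vs 40 | 16.6 vs 17.1 | 54.0 vs 53.9 |
| HGI-Kefir vs LGI-Kefir | same | 70 vs 41 | 7.9 vs 16.6 | 75.8 vs 54.0 |
| HGI-Kefir vs LGI-Milk | changes | 70 vs 40 | 7.9 vs 17.1 | 75.8 vs 53.9 |

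The second pair is the GI contrast in the sense of the design, although fat and carbohydrate move with GI. The third pair adds the change of drink.

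**2. The plan's own figure.** The 21 in Section 4.1 cannot be reproduced without an SD. Solving backwards for a two-sided paired t-test at 0.05 with n = 21 and 80% power gives a standardised paired difference of 0.643. Reading the 5% as five percentage points, the implied SD of the paired difference is 5/0.643 = 7.8 points. This is an assumption, not a planned value.

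**3. Power for one kefir comparison at n = 22.** Power = P(|T| > t(1 - a/2; 21)), where T is noncentral t with 21 degrees of freedom and noncentrality 0.643 x sqrt(22) = 3.016.

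| Adjustment | Per-test alpha | Critical t | Power | N for 80% |
|---|---|---|---|---|
| None, or tested first in a fixed order | 0.05 | 2.080 | 82.0% | 21 |
| Bonferroni, two contrasts | 0.025 | 2.414 | 72.3% | 26 |
| Bonferroni, three pairs | 0.0167 | 2.601 | 66.0% | 29 |

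The total drop is 82.0 - 66.0 = 16.0 points. Of this, 82.0 - 72.3 = 9.7 points come from having two comparisons at all, and 72.3 - 66.0 = 6.3 points from the third pair.

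**4. Holm.** Its power depends on the other pairs, so it was simulated: n = 22, equal within-woman variance, kefir effect 0.643, and the GI effect (HGI-Kefir minus LGI-Kefir) in SDs of the paired difference.

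| GI effect | Bonferroni, three | Holm, three | Holm, two |
|---|---|---|---|
| -1.0 | 66% | 75% | 82% |
| -0.643 | 66% | 70% | 78% |
| -0.3 | 66% | 67% | 73% |
| 0 | 66% | 70% | 72% |
| 0.643 | 66% | 80% | 80% |
| 1.0 | 66% | 82% | 82% |

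Once Holm is used, dropping the third pair adds 0 to 2 points when the GI effect is zero or has the same sign as the kefir effect, and about 6 to 8 points when the signs are opposite.

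**5. Sensitivity to the assumed SD.** The gain from three to two Bonferroni comparisons at n = 22, for a five-point difference:
- SD 5: 98.5 - 97.5 = 1.0 point
- SD 8: 69.6 - 63.2 = 6.4 points
- SD 10: 48.5 - 41.8 = 6.7 points
- SD 15: 22.1 - 17.5 = 4.6 points

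**6. Time points.** Section 3.3 lists seven postprandial ratings. If the Bonferroni family spans them, it holds 3 x 7 = 21 tests, or 2 x 7 = 14 with two contrasts. At the same standardised difference, power for one comparison is 36.4% or 42.1%.

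**The case against.** A reader might infer that the plan certainly spends a third of its error rate on a useless pair, and that the kefir comparison loses 16 points on every primary outcome for nothing. The documents do not support that reading, for four reasons.

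- **The family is not defined.** Three pairs is the natural reading of unrestricted post hoc tests on three meals, but Section 4.2 does not say so. If time points are included, the undefined family matters more than the third pair.
- **The scope is narrow.** Bonferroni is tied to the time x meal interaction. Lunch intake and AUC each give one value per woman and meal, so no such interaction exists for them and no Bonferroni loss is shown. Their gap is that no follow-up is named. The 66% describes one paired comparison and does not model the interaction test that precedes it.
- **Most of the drop is not due to the third pair.** It accounts for about 6 of the 16 points.
- **The third pair is not meaningless.** It compares a high-GI meal with kefir against the low-GI milk meal. No section poses that question, but it can be described. The deeper limit is the missing high-GI milk meal, because the objective covers kefir with either kind of meal.

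Dropping the pair is also not the only remedy. With three meals, a significant omnibus F followed by unadjusted pairwise tests holds the family-wise error near 5% within one outcome or time point (0.049 to 0.051 in simulation under sphericity). It gives the kefir pair 73% to 82% power over the same GI effects.

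All of this stands and limits the claim. It leaves two facts in place: the stated adjustment is dominated, and HGI-Kefir versus LGI-Milk isolates neither factor.

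**Conclusion.** The point holds in a limited form. That Holm rejects at least as much as single-step Bonferroni at the same family-wise error needs no assumption about SD or effect. Holm over two contrasts also tests each at 0.025 or above, so for those contrasts it rejects whatever three-pair Bonferroni would at 0.0167.

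The size does rest on assumptions: a three-pair family, a standardised difference of 0.643, two-sided testing, and equal within-woman variance for the simulated figures. On that basis, kefir power in the interaction follow-up rises from about 66% to 72-82%. This affects the efficiency and clarity of the analysis; it does not threaten the validity of the trial.

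**What to change.** In Section 4.2, replace the Bonferroni sentence with text to this effect: meals are compared by two contrasts, LGI-Kefir minus LGI-Milk and HGI-Kefir minus LGI-Kefir, with Holm-adjusted p-values; HGI-Kefir versus LGI-Milk is shown descriptively, without a test. State whether the Holm family spans the time points. Apply the same two contrasts after the one-way ANOVA for AUC and lunch intake.

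The cost is a few lines of SAP text and no new data. The third pair loses its p-value, and the Holm step has to be computed by hand from the SPSS output. Since Section 4.1 already reports completion with 22 women, the change should be labelled post hoc if results have been seen.
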